5.2 Statistical Methods for Data Analysis

Descriptive statistics such as mean and standard deviation (or median and interquartile range) will be used to summarize data in raw scale or change from baseline per visit.

The primary outcome, change in log₁₀ TG at Week 16 from baseline, and continuous secondary outcomes will be compared between ISIS 304801 and placebo groups using either two-sample t-test or Wilcoxon rank sum test as appropriate based on change from Baseline at Week 16. Changes from baseline based on tertiary/exploratory outcomes as well as change on log₁₀ TG at Week 16 will be examined using either one-sample t-test or Wilcoxon signed rank test as appropriate.

Repeated measures analysis of covariance using linear mixed models will be conducted in order to investigate trends on selected response variables and to compare active and placebo group while possible covariates are taken into account. There are three possible covariates: (1) Baseline level of the outcome of interest, (2) Baseline level of ApoCIII, and (3) Change in ApoCIII before and after the 16 week active drug intervention.

Inclusion of covariates will be checked using linear mixed models by checking Akaike Information Criteria (AIC) with inclusion of one covariate at a time

Analyses will include all available data even if patients do not adhere to their assigned treatments. Additional analyses will examine the effect of adherence to study results. We will also investigate the effect of missing data on the results using standard methods for missing data.

A p-value of 0.05 or less is considered significant.

6. Experimental Plan

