3.1 Inclusion Criteria

1. Age \geq 18 years at enrollment (the time of informed consent, week -1)
2. Fasting TG levels \geq 500 mg/dL (\geq 5.7 mmol/L) at enrollment. If the fasting TG value is $<$ 500 mg/dL ($<$ 5.7 mmol/L) but \geq 350 mg/dL (\geq 4.0 mmol/L) up to two additional tests may be performed in order to qualify, and a single level \geq 500 mg/dL will permit enrollment.

OR

3. Fasting TG levels \geq 200 mg/dL (2.6mmol/L) with a hemoglobin A1C over 7%
4. Willing to maintain their customary physical activity level and to follow a diet moderate in carbohydrates and fats with a focus on complex carbohydrates and replacing saturated for unsaturated fats
5. Clinical diagnosis of lipodystrophy based on deficiency of subcutaneous body fat in a partial fashion assessed by physical examination, and low skinfold thickness in anterior thigh by caliper measurement: men (\leq 10mm) and women (\leq 22 mm), plus one of the following:

a) Genetic diagnosis of familial PL (e.g., mutations in LMNA, PPAR- γ , AKT2, or PLIN1 genes)

OR

b) Family history of familial PL or abnormal and similar fat distribution PLUS 1 minor criterion (below), OR

c) 2 minor criteria (below) in the absence of genetic diagnosis of family history

MINOR Criteria

- a. Diabetes mellitus with requirement for high doses of insulin, eg, requiring \geq 200 U/day, \geq 2 U/kg/day, or currently taking U-500 insulin
- b. Presence of acanthosis nigricans on physical examination
- c. History of polycystic ovary syndrome (PCOS) or PCOS-like symptoms (hirsutism, oligomenorrhea, and/or polycystic ovaries)
- d. History of pancreatitis associated with hypertriglyceridemia
- e. Evidence of non-alcoholic fatty liver disease
 - Hepatomegaly and/or elevated transaminases in the absence of a known cause of liver disease or
 - Radiographic evidence of hepatic steatosis (e.g., on ultrasound or CT)

6. Satisfy one of the following:

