5.1 Sample Size Justification

The primary outcome variable is the change in log₁₀ fasting triglycerides from before treatment to 16 weeks of active drug treatment compared to placebo groups.

Preliminary data are available for 28 patients treated with ISIS 304801 and 24 treated with placebo. For the ISIS 304801 group, these data show a difference from baseline to follow-up of -423 (SD 400, 95% CI -578 to -268) mg/dL and -0.485 (SD 0.221, 95% CI -0.57 to -0.40) log₁₀ mg/dL. Converting the difference in log₁₀ mg/dL to a percent change [$100 \times (10^{-0.485} - 1)$] results in a percent change of -67% (95% CI -73% to -60%). For the placebo group, the absolute change is -12 (SD 406, 95% CI -12 to 184) mg/dL and -0.011 (SD 0.224, 95% CI -0.105 to 0.084) log₁₀ mg/dL. The percent change for the placebo group is -3% (95% CI -21% to 21%).

For comparison of placebo and ISIS 304801 we have chosen a SD of 0.25 log₁₀ mg/dL and a difference of 0.50 log₁₀ mg/dL. A trial with 5 patients in each group has 79% power to detect a difference of 0.50 log₁₀ mg/dL triglycerides in the change from baseline to follow-up between the ISIS and placebo groups, assuming a SD of 0.25 log₁₀ mg/dL and a two-sided significance level of 0.05.

Where preliminary data were available, sample size calculations were performed for secondary and tertiary study outcomes in addition to the primary outcome. The preliminary data and power estimates for a sample size of 10 subjects (using one-sample t-test for off versus on drug comparisons) are summarized in the table below. Based on these calculations, the study should be adequately powered to detect differences in total body insulin sensitivity, hepatic insulin sensitivity, fasting glucose, apoC-III serum level, HDL-C, VLDL-C, and apolipoprotein B48.

Based on these calculations, we plan to enroll a maximum of 20 patients, with a goal of 10 patients completing the study (defined as completing 16 weeks of active drug treatment). The accrual ceiling of 20 is planned because subjects will consent to the study prior to screening, thus we are accounting for up to 10 screen failures in the accrual ceiling.

	Outcome	Model	Treatment	Treat- ment Duration	Mean of Δ on-off drug (SD)	Power
Primary outcome	Absolute change log[serum triglycerides] (mg/dL)	High TG +/- diabetes and/or fibrate	ApoCIII ASO 300 mg/wk	16 wk	-0.48 (0.22)	>0.95
	% change serum triglycerides (%)	High TG +/- diabetes and/or fibrate	ApoCIII ASO 300 mg/wk	16 wk	-63 (20)	>0.95

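### The primary comparison does not condition on baseline log10 TG and leaves the test open; baseline adjustment rests on an AIC-selected secondary model

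*Combined protocol and SAP*

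**What the plan says.** Section 5.1 defines the outcome: "The primary outcome variable is the change in log₁₀ fasting triglycerides from before treatment to 16 weeks of active drug treatment compared to placebo groups". For the between-group calculation it states that "we have chosen a SD of 0.25 log₁₀ mg/dL and a difference of 0.50 log₁₀ mg/dL", and concludes that "A trial with 5 patients in each group has 79% power to detect a difference of 0.50 log₁₀ mg/dL triglycerides" at a two-sided 0.05 level.

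Section 5.2 gives the test. Change in log10 TG, like the other continuous endpoints, "will be compared between ISIS 304801 and placebo groups using either two-sample t-test or Wilcoxon rank sum test as appropriate". The quantity tested is each patient's Week 16 value minus baseline. No covariate is attached to either test, and no criterion is given for choosing between them.

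The same section adds a repeated-measures analysis of covariance by linear mixed model, which also compares the arms. It covers selected response variables that are not named. The first of its three possible covariates is "1) Baseline level of the outcome of interest". Whether a covariate is included is judged by AIC, one covariate at a time.

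Two design features bear on imbalance. Section 4.1 stratifies randomization by use of lipid-lowering medication, not by TG. Section 3.1 has two TG entry routes: 500 mg/dL or more, or at least "200 mg/dL (2.6mmol/L) with a hemoglobin A1C over 7" percent. Neither has an upper TG limit.

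**The concern.** A change score fixes the baseline slope at 1. If the true slope of Week 16 log10 TG on baseline is below 1, the arm that happens to start higher is expected to fall further whatever the treatment does. With 5 patients per arm, a wide entry range and no stratification on TG, some imbalance should be expected. The reader of the one trial that is run would then be unable to separate that part from the drug effect.

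The mixed model does not settle this. It is not called primary, log10 TG is not named among its response variables, and baseline may be dropped on AIC. Another candidate covariate is the change in apoC-III over treatment, which is measured after randomization and is the drug's direct target; a model that includes it would not give a baseline-adjusted estimate of the total drug effect. So the plan guarantees no baseline-adjusted estimate for the primary outcome.

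The open choice of test is a second gap in the same sentence. The sample size was justified for one of the two permitted tests only.

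**Working it through.** **Inputs from Section 5.1:** 5 per arm; difference 0.50 log10 mg/dL; SD of change 0.25; two-sided alpha 0.05.

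**Inputs not in the documents:** the correlation ρ between baseline and Week 16 log10 TG, and the baseline log10 SD. I assume normal data and equal SDs at the two visits, and take ρ from 0.3 to 0.9.

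**1. The plan's own figure.** Standard error of the difference = 0.25 × √(2/5) = 0.158. Noncentrality = 0.50 / 0.158 = 3.16; df = 8; critical t = 2.306. Power from the noncentral t distribution = 79.05%. The stated 79% is reproduced, and it is the power of the two-sample t-test.

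**2. Share of an imbalance that reaches the estimate.** With equal SDs the slope of Week 16 on baseline is ρ. The expected shift in the change-score difference is −(1 − ρ) × (baseline difference between arms). With the SD of change held at 0.25:

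- baseline SD = 0.25 / √(2(1 − ρ))
- standard error (SE) of the baseline difference = baseline SD × √(2/5)
- shift at a one-SE imbalance = (1 − ρ) × that SE

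At ρ = 0.5: baseline SD 0.250, SE 0.158, shift 0.5 × 0.158 = 0.079, which is 16% of 0.50.

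**3. Power of ANCOVA.** Simulation of at least 40,000 trials per ρ, 5 per arm, effect −0.50, ANCOVA with 7 df. The t-test stays at about 79% throughout.

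| ρ | Baseline SD | SE of baseline difference | Shift at one SE | Share of 0.50 | ANCOVA power |
|---|---|---|---|---|---|
| 0.3 | 0.211 | 0.134 | 0.094 | 19% | 87% |
| 0.5 | 0.250 | 0.158 | 0.079 | 16% | 83% |
| 0.7 | 0.323 | 0.204 | 0.061 | 12% | 78% |
| 0.8 | 0.395 | 0.250 | 0.050 | 10% | 76% |
| 0.9 | 0.559 | 0.354 | 0.035 | 7% | 74% |

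At ρ = 0.65 ANCOVA has just under 80% power, so break-even lies near 0.65 to 0.7. Type I error was about 5% for both methods at every ρ, and the mean change-score estimate was −0.50 to within 0.002.

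**4. The rank-sum alternative.** With 5 against 5 there are 252 equally likely rank allocations. The largest two-sided exact rejection region not above 5% holds 8 of them: 8/252 = 3.2%. The next step would be 14/252 = 5.6%. Simulated power at the design values is about 68%, so this permitted test costs about 11 points against the stated 79%. These figures do not depend on ρ.

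**The case against.** **The change score already uses baseline.** This stands. A reader might infer that an imbalance passes in full into the estimate, or that the plan ignores baseline. The documents support neither: baseline is subtracted from every patient, only (1 − ρ) of an imbalance remains, and Section 5.2 does list the outcome's baseline as a candidate covariate of the mixed model.

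**There is no unconditional error.** This also stands. Over randomization the t-test is unbiased and holds its level. At ρ = 0.5 the one-SE shift of 0.079 is half the estimate's own standard error of 0.158, so the confidence interval already allows for it on average. What remains is that a known, measured source of error in the realised trial goes unused.

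**The wide entry range works against ANCOVA.** With SD of change at 0.25, a wider baseline spread implies a higher ρ: a baseline log10 SD of 0.40 gives ρ = 1 − 0.25² / (2 × 0.40²) = 0.80. Section 5.1 offers a rough hint. Its absolute change is −423 (SD 400) mg/dL and its percent change is −63 (SD 20). Suppose baseline is lognormal and independent of percent change. Mean baseline is then 423 / 0.63 = 671, and mean squared baseline is (400² + 423²) / (0.63² + 0.20²) = 775,759. The ratio 775,759 / 671.4² = 1.72 gives a log10 SD of √(ln 1.72) / ln 10 = 0.32, and so ρ of about 0.69. That is at break-even. It rests on strong assumptions and on patients with hypertriglyceridemia rather than partial lipodystrophy, but it rules out presenting ANCOVA as a way to gain power.

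**The choice of test is a separate matter.** True in logic, but it sits in the same sentence of Section 5.2 and is cured by the same edit.

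**Conclusion.** The concern holds in a limited form. The primary comparison does not condition on baseline log10 TG, baseline adjustment is left to a secondary model with AIC-selected covariates, and the test itself is not fixed. The conditional shift for a one-standard-error imbalance is 0.035 to 0.094 log10 for ρ from 0.9 down to 0.3, so it would distort the size of the estimate modestly against a planned effect of 0.50. It does not make the planned test invalid. The power statement is correct for the t-test and about 11 points too high for the exact rank-sum test.

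A reader might go on to infer that adjustment will raise power. That is not established: it does so only for ρ below about 0.65 to 0.7, and the documents give neither ρ nor the baseline log10 SD. All the ρ-dependent figures assume normality, equal SDs at the two visits and an SD of change of 0.25. The case for the change is a single pre-specified estimate that accounts for baseline, not extra power.

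**What to change.** In Section 5.2, name one primary analysis: an ANCOVA of Week 16 log10 TG on arm and baseline log10 TG, with baseline as a fixed covariate outside any AIC selection. Keep the unadjusted t-test on change as a sensitivity analysis. Remove the rank-sum alternative for the primary outcome. If the sponsor prefers the change-score t-test as primary, it should be fixed as the only primary test, with the ANCOVA as the named sensitivity analysis. In either case Section 5.1 should say which test its 79% refers to.

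The cost is a few lines of wording; baseline TG is already collected. The statistical price is one of 8 degrees of freedom and a slope estimated from 10 patients. Against the t-test's 79%, ANCOVA gains about 8 to 9 points at ρ = 0.3, is level near 0.65 to 0.7, and loses about 3 points at 0.8 and 5 at 0.9.

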The purpose of this study is to determine if apoC-III reduction using an ASO to apoC-III (ISIS 304801) will reduce triglycerides and improve insulin resistance, diabetes, and hepatic steatosis in patients with lipodystrophy. The primary hypothesis to be tested is:

1. ISIS 304801 will reduce log₁₀ fasting serum triglycerides.

Secondary and tertiary hypotheses to be tested are:

2. ISIS 304801 will improve glucose metabolism by improving insulin resistance.
3. ISIS 304801 will reduce hepatic steatosis.
4. ISIS 304801 will improve cardiovascular risk markers.

We will also explore the mechanism of action of apoC-III ASO by studying lipoprotein lipase activity and lipoprotein particle distribution.

Methods

This study will enroll up to 20 patients with partial lipodystrophy with a goal of 10 study completers. The study will be conducted in two phases. The first is a 16-week, randomized, double-blind, placebo-controlled design. Subjects will be treated with ISIS 304801 at a target dose of 300 mg per week or placebo. Following this phase, all subjects will enter a 12 month open-label extension in which they will receive active drug. Patients who experience benefit (triglyceride lowering $\geq 50\%$) may receive an additional 12 months of open-label drug (up to 24 months, total). Measurement of the primary outcome (serum triglycerides) and key secondary outcomes will be performed at baseline prior to the intervention, after 16 weeks (primary and secondary outcomes) of blinded drug or placebo, and after an additional 4 months of active drug in subjects initially randomized to placebo.

STUDY GLOSSARY

Abbreviation	Definition
2'-MOE	2'-O-(2-methoxyethyl)
AE	adverse event
ALT	alanine aminotransferase (SGPT)
ANA	antinuclear antibody
apoA1	apolipoprotein A1
apoB	apolipoprotein B
apoC-III	apolipoprotein C-III
apoE	apolipoprotein E
aPTT	activated partial thromboplastin time
ASO	antisense oligonucleotide
AST	aspartate aminotransferase (SGOT)
BMI	body mass index
BP	blood pressure
DEXA	dual-energy X-ray absorptiometry
DSMB	Data and Safety Monitoring Board
EKG	electrocardiogram
eCRF	electronic Case Report Form
FPG	fasting plasma glucose
FPL	familial partial lipodystrophy
FSH	follicle-stimulating hormone
GCP	Good Clinical Practice
HBsAg	hepatitis B surface antigen
HBV	Hepatitis B virus
HbA1C	Hemoglobin A1C
HCV	hepatitis C virus
HDL-C	high-density lipoprotein cholesterol
hERG	human ether-a-go-go
HIV	human immunodeficiency virus

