1.2 Secondary/Tertiary Objectives

To evaluate the efficacy of 16 weeks of ISIS 304801 as compared to placebo (between group comparison) on additional lipid, glycemic, hepatic, and cardiovascular parameters (see Outcome Measures), as well as safety and tolerability of ISIS 304801. In addition, the effects of ISIS 304801 (defined as tertiary outcomes) as compared to immediately prior to treatment (pre-post within subject comparison) for 16 weeks on these outcomes will be evaluated.

2. Introduction

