4.2 Outcome Measures

4.2.1 Primary outcome:

Efficacy of 16 weeks of ISIS 304801 as compared to placebo (between group comparison) on the change in log₁₀ fasting triglycerides (TG).

4.2.2 Secondary outcomes:

Efficacy of 16 weeks of ISIS 304801 as compared to placebo (between group comparison) on:

Lipids

- Percent change in fasting TG
- Absolute change in fasting TG
- Change in lipolysis rate measured using stable isotope tracers
- Change from baseline in liver volume and hepatic steatosis (as assessed by magnetic resonance imaging [MRI] and magnetic resonance spectroscopy [MRS])
- Lipoprotein lipase activity

Glycemic

- Change in total body insulin sensitivity using the hyperinsulinemic euglycemic clamp
- Change in hepatic glucose production and hepatic insulin sensitivity using stable isotope tracers in combination with the hyperinsulinemic euglycemic clamp
- Change in hemoglobin A1c (HbA1c)
- Change in fasting plasma glucose

Safety

- Safety and tolerability of ISIS 304801
- Prospectively adjudicated acute pancreatitis events (Atlanta classification) and Major Adverse Cardiovascular Events (MACE)

Pharmacokinetic

- Plasma ISIS 304801 level

4.2.3 Tertiary/Exploratory outcomes:

Efficacy of 16 weeks and 16 months of ISIS 304801 as compared to immediately prior to treatment (pre-post within subject comparison) on:

Lipids

- Change in other fasting lipid measurements: high-density lipoprotein cholesterol (HDL-C), low-density lipoprotein cholesterol (LDL-C), total cholesterol (TChol), very low-density lipoprotein cholesterol VLDL-C, non-HDL-C, apolipoprotein B (apoB), apolipoprotein B-48 (apoB48), apolipoprotein A1 (apoA1), apolipoprotein CIII (apoC-III; total, chylomicron, VLDL, LDL and HDL), and free fatty acids
- Change in lipoprotein particle size/number by nuclear magnetic resonance (NMR)
- Triglyceride (and other lipid particle) clearance following mixed meal testing

Glycemic

- Change in 24-h glucose (using 7-point plasma blood glucose)
- Change in fasting and area under the curve for insulin and C-peptide during mixed meal testing
- Reduction in insulin use

Adipose tissue

- Change in skinfold thickness and dual-energy X-ray absorptiometry (DEXA)
- Change in abdominal VAT and SAT volumes
- Change in adiponectin and leptin
- Change in body weight and waist circumference

Cardiovascular

- Carotid intima-media thickness (by ultrasound)
- Coronary artery wall thickness and diameter change after hand-grip exercise (by MRI)

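### Section 1.2 promises a placebo comparison on cardiovascular and additional lipid parameters, but 4.2.3 lists the cardiovascular imaging markers and other tertiary outcomes as pre-post only, and 5.2 names no between-group test for them

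*Combined protocol and SAP*

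**What the plan says.** **Objective.** Section 1.2 sets out to evaluate 16 weeks of drug "as compared to placebo (between group comparison) on additional lipid, glycemic, hepatic, and cardiovascular parameters (see Outcome Measures"). It then adds that the effect "as compared to immediately prior to treatment (pre-post within subject comparison) for 16 weeks on these outcomes will be evaluated". The Precis (Aim) lists among its secondary and tertiary hypotheses that "ISIS 304801 will improve cardiovascular risk markers".

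**Outcome list.** Section 4.2.2 gives the between-group comparison to percent and absolute triglyceride change, lipolysis, liver volume and fat, lipoprotein lipase activity, glycemic measures, safety (including major cardiovascular events) and drug level. Section 4.2.3 opens with "Efficacy of 16 weeks and 16 months of ISIS 304801 as compared to immediately prior to treatment (pre-post within subject comparison) on" and places under that heading "Carotid intima-media thickness (by ultrasound"), the coronary wall and diameter measures, and "Change in other fasting lipid measurements: high-density lipoprotein cholesterol (HDL-C), low-density lipoprotein cholesterol (LDL-C), total cholesterol (TChol") with the rest of the fasting lipid panel. Lipoprotein particles, adipose measures and patient-reported outcomes are there too. The last line of 4.2.3 mentions a placebo comparison, but only for the primary and secondary outcomes.

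**Analysis.** Section 5.2 assigns two-sample t or rank sum tests to the primary and continuous secondary outcomes. For the tertiary tier it says: "Changes from baseline based on tertiary/exploratory outcomes as well as change on log₁₀ TG at Week 16 will be examined using either one-sample t-test" or the signed rank test. A further paragraph plans mixed models that compare active and placebo on a selection of responses it does not list. Section 4.1 has a line for placebo-versus-drug comparisons (C vs H) that is not tied to any outcome; its figure is not available to us.

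**The concern.** The objective is randomised and blinded; the analysis named for these outcomes is neither. A one-sample test attributes all change to the drug. The plan contains other possible sources of change: diet counselling 2-8 weeks before entry that continues at visits (6.1, Appendix A), and entry on a high triglyceride value, where one qualifying result among up to three tests is enough (3.1). For placebo-first patients the on-drug interval is also open label, which matters for pain, hunger and quality of life.

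At stake is whether the cardiovascular hypothesis in the Precis can be addressed against placebo. The only cardiovascular item with a between-group comparison is major events, listed as safety, and these are not risk markers.

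**Working it through.** **1. Are control data scheduled?** Appendix A, rows at Weeks 1 and 16, none restricted by arm at those visits:

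| Measurement | Week 1 | Week 16 |
|---|---|---|
| cIMT | yes | yes |
| Liver/heart MRI | yes | yes |
| DEXA, mixed meal, 7-point glucose | yes | yes |
| Hunger, pain, quality of life | yes | yes |
| Skinfold | screening only | no |
| Fasting lipids | row not visible in the text available | inferred |

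**2. Reproduce the plan's power figures.** Noncentral t, two-sided 0.05.
- Two-sample, 5 per arm: ncp = (Δ/SD)/√(2/5), df = 8. Primary (5.1): Δ = 0.50, SD = 0.25, ncp = 2.0/0.632 = 3.16, power 0.791. The plan states 79%. Reproduced.
- One-sample, n = 10: ncp = (Δ/SD)×√10, df = 9. HDL-C, 13.3/10.1 = 1.317, ncp = 4.16, power 0.958 (plan: >0.95). VLDL-C, 77/60 = 1.283, ncp = 4.06, power 0.949 (plan: 0.95). ApoB-48, 0.44/0.43 = 1.023, ncp = 3.24, power 0.821 (plan: 0.82). Reproduced.

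**3. The same outcomes against placebo, 5 v 5.** Assumptions: zero mean placebo change and the tabulated SD in both arms; the range is for SD ×1.2 to ×0.8.

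| Outcome | Pre-post, n=10 | 5 v 5 | Range |
|---|---|---|---|
| ApoC-III | >0.99 | 0.81 | 0.66-0.94 |
| HDL-C | 0.96 | 0.45 | 0.33-0.63 |
| VLDL-C | 0.95 | 0.43 | 0.32-0.61 |
| ApoB-48 | 0.82 | 0.30 | 0.22-0.43 |
| LDL-C | 0.46 | 0.15 | 0.12-0.21 |

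The documents give no effect size or SD for cIMT or the coronary measures, so their power cannot be computed.

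**4. How far could drift mislead the pre-post test?** With no drug effect and a non-drug drift of f SDs of the change, the one-sample test at n = 10 has ncp = f√10.
- f = 0.3 (assumed): ncp = 0.95, rejection rate 13.6%.
- f = 0.5 (assumed): ncp = 1.58, rejection rate 29.3%.
- Placebo log₁₀ triglycerides in 5.1: 0.011/0.224 = 0.049, ncp = 0.16, rejection rate 5.2%.
- Placebo absolute triglycerides in 5.1: 12/406 = 0.030, ncp = 0.09, rejection rate 5.1%.

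The nominal rate is 5%.

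**The case against.** A reader might infer that these outcomes are tested only without control, and that the placebo data are collected and then discarded. The documents do not support that. The mixed models in 5.2 compare arms on some responses, descriptive change from baseline is planned per visit, and the C vs H line in 4.1 may reach these outcomes. What stands is that no between-group test is specified for them and that the mixed-model variables are unnamed.

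Section 1.2 also points to the outcome list for detail and labels the pre-post effects as tertiary, so 4.2.3 and 5.2 follow a tiering that 1.2 itself introduces. That is fair, but it does not remove the placebo comparison that the same section promises for cardiovascular parameters. The lipid part of the promise is partly met, through triglycerides, lipolysis and lipase activity. The gap is clearest for cardiovascular imaging.

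The table in 5.1 appears to place apoC-III and HDL-C among the secondary outcomes, which would give them the two-sample test, whereas 4.2.3 lists them as tertiary. The table may be broken in the text available, but the tier is unclear as it reads.

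It is tempting to read the 5.2 sentence as putting placebo-first patients' change on placebo into the one-sample triglyceride test. Sections 1.2 and 4.2.3 anchor pre-post change to the time just before treatment, and the Precis schedules measurement after four months of active drug in placebo-first patients. The 5.2 wording is loose; it does not establish that error.

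Finally, selection on triglycerides is not selection on cIMT or pain, the diet advice before baseline acts partly as a run-in, and pre-post analysis of exploratory outcomes in a rare disease is a disclosed choice with more power. All of this stands. It bears on the likely size of the bias, and it is a reason to keep the pre-post analysis.

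**Conclusion.** The point holds as a mismatch between the objective and the specified analysis, at the level of a cheap improvement. It is firm for cIMT and the coronary MRI measures. It extends to the other tertiary outcomes with Week 1 and Week 16 values; for fasting lipids that rests on an inference about Appendix A, and skinfold drops out.

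No size can be put on the bias. The 14% and 29% figures depend wholly on assumed drifts. The triglyceride placebo data give about 5%, but say little about imaging or patient-reported measures. A claim that the pre-post results will be seriously misleading would go beyond the documents. The primary analysis and the two-sample tests of the continuous secondary outcomes are unaffected.

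**What to change.** - In 4.2.3 and 5.2, report the Week 16 active-minus-placebo difference in change from baseline, with 95% CI, as an exploratory estimate for each tertiary outcome measured in both arms. Keep the pre-post analysis as supportive.
- Name the response variables for the mixed models.
- Define the pre-post interval as Weeks 1-16 for active-first patients and Weeks 16-32 for placebo-first patients.
- Align the tier of HDL-C and apoC-III between 4.2.3 and the 5.1 table.
- Limit the 5.1 statement of adequate power to the pre-post test.

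If the sponsor wants pre-post only, 1.2 should be amended to say so.

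The cost is wording and extra output from measurements already scheduled. The downside is precision: intervals at 5 v 5 will be wide and few tertiary differences are likely to reach significance, which is why they should be presented as estimates.
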